5.6.9 Dose Modification

Subjects should not modify the study medication application procedure or frequency unless instructed to do so by the investigator. All application modifications must be reported on the appropriate CRF page.

If any significant study medication intolerance or safety issue occurs, after consulting with the Medical Monitor, the investigator or designee may direct the subject to reduce the study medication application frequency. If the subject cannot perform QD applications to a specific Target cNF(s), the subject may continue study medication treatment of <10 Target cNFs selected by the investigator for the duration of the study after consultation and approval from the Medical Monitor. If the subject cannot perform QD applications to any Target cNF for a total of 25 days,

the subject must be removed from the study. The total of 25 days applies to individual Target cNFs and is not an aggregate of non-treatment days of each Target cNF. Each Target cNF that meets or exceeds 25 total days of non-treatment cannot restart treatment. All 10 Target cNFs must be evaluated at each visit per protocol requirements regardless of study medication application frequency.

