5.4 Subject discontinuation from the study

Subjects will be informed that they are free to withdraw from the study at any time and for any reason.

The investigator may remove a subject from the study if, in the investigator's opinion, it is not in the best interest of the subject to continue the study. The investigator must remove a subject from the study if the subject experiences:

- A Serious Adverse Event the investigator defines as related to the study medication, regardless of the intensity of the event
- A non-serious adverse event the investigator defines as related to study medication that has a severity of severe and requires treatment to resolve.

Examples of other reasons subjects may be discontinued from the study are a change in compliance with an inclusion or exclusion criterion, occurrence of AEs, occurrence of pregnancy or use of a prohibited therapy. Notification of discontinuation will immediately (within 24 hours) be made to the study monitor.

All withdrawn subjects with ongoing AEs will be followed as appropriate.

The study may be discontinued at the discretion of NFllection. Some examples of reasons for discontinuation are the occurrence of the following:

- Increased frequency, severity, or duration of known AEs
- Medical, regulatory, or ethical reasons affecting the continued performance of the study
- Difficulties in the recruitment of subjects.

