5.4.3 Early Termination Visit

The investigator should complete the following study procedures for randomized subjects who prematurely discontinue from the study:

- For subjects who discontinue from the study prior to Visit 8, complete the Visit 8 procedures
- For subjects who complete Visit 8 and discontinue from the study prior to Visit 9 complete the Visit 9 procedures.

Detailed instructions for documenting subjects who prematurely discontinue from the study will be included in the CRF completion guidelines.

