15. Review the study instructions, including application technique and Target cNF locations, with the subject

16. Schedule the next study visit.

6.2.7 Visit 7/Day 141/Week 20: 140 (± 4 days) after Visit 2 (QD treatment)

Subjects should not apply the study medication within 6 hours prior to this visit.

At Visit 7, the investigator or designee will perform the following procedures:

1. Query the subject in a non-directive manner about any changes in her/his health since the previous visit and report all AEs as appropriate
2. Query the subject about any changes in her/his concomitant therapies since the previous visit and report changes as appropriate
3. Confirm the subject has followed all study instructions
4. Perform a urine pregnancy test for WOCBP
5. Confirm the location of each Target cNF
6. **FOR EACH TARGET cNF:**
 - Perform a PTA
 - Have the subject perform an SSA
 - Measure the dimensions
7. Have the subject perform an LTA of the symptoms for each Target cNF
8. The investigator will perform an LTA of the signs for each Target cNF
9. Weigh study medication
10. Collect and dispense study medication as appropriate
11. Review the study instructions, including application technique and Target cNF locations, with the subject
12. Schedule the next study visit.

6.2.8 Visit 8/Day 183/Week 26 (End of QD treatment; start of no treatment follow-up; early termination if subject discontinues from the study prior to Visit 8)

This visit must occur 182 days (± 4 days) after Visit 2.

Subjects should not apply the study medication within 6 hours prior to this study visit.

At this visit, the investigator or designee will perform the following procedures:

1. Query the subject in a non-directive manner about any changes in her/his health since the previous visit and report all AEs as appropriate
2. Query the subject about any changes in her/his concomitant therapies since the previous visit and report changes as appropriate
3. Confirm the subject has followed all study instructions
4. Measure vital signs
5. Collect samples for clinical laboratory tests
6. Perform a urine pregnancy test for WOCBP
7. Confirm the location of each Target cNF
8. Perform a PTA for each Target cNF
9. Have the subject perform a SSA for each Target cNF
10. Have the subject perform a PROM for each Target cNF
11. Have the subject perform an LTA of the symptoms for each Target cNF
12. The investigator will perform an LTA of the signs for each Target cNF

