9.3 Statistical Analyses

9.3.1 General Approach

All randomized and treated subjects will be assessed in analyses of safety and efficacy. Descriptive statistics will be produced on relevant screening and baseline data and on demographic characteristics. Safety and efficacy endpoints will be summarized descriptively by treatment (when applicable) and for all subjects combined and may be analyzed using appropriate parametric or nonparametric inference tests. Comparisons between NFX-179 treated cNFs and vehicle treated cNFs will also be performed as described below. Summaries and analyses will be based primarily on non-missing data.

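### Subjects who stop all study medication under 5.6.9 or 5.4 are removed from the study, so their Day 182 tumor values are not collected and the observed-cases primary analysis either omits them or uses an early value

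*Combined protocol and SAP*

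**What the plan says.** Section 5.6.9 sets two courses for a subject who cannot keep up daily application. If some tumors cannot be treated, "the subject may continue study medication treatment of <10 Target cNFs selected by the investigator for the duration of the study", with Medical Monitor approval, and follow-up is unchanged: "All 10 Target cNFs must be evaluated at each visit per protocol requirements regardless of study medication application frequency". If no tumor can be treated for 25 days, "the subject must be removed from the study. The total of 25 days applies to individual Target cNFs and is not an aggregate". The rule names no cause for the missed applications.

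Section 5.4 adds a second mandatory exit, opening with "The investigator must remove a subject from the study if the subject" and listing a related SAE and "A non-serious adverse event the investigator defines as related to study medication that has a severity of severe and requires treatment to resolve".

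For anyone leaving early, 5.4.3 says: "For subjects who discontinue from the study prior to Visit 8, complete the Visit 8 procedures". Those procedures include tumor dimensions, and the heading of 6.2.8 names Visit 8 as the early-termination visit. The body of 6.2.8 fixes its timing: "This visit must occur 182 days (± 4 days) after Visit 2".

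Under 9.3.2, primary and secondary efficacy analyses use the OC population: ITT subjects who have efficacy observations at Visit 8, with nothing imputed. There are two sensitivity analyses, per-protocol (a subset of OC) and ITT with LOCF. Mixed-model or multiple imputation is optional. A supplemental ITT analysis of subject Responders counts terminations before Visit 8 for treatment-related adverse events as non-response.

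**The concern.** The endpoint is tumor volume after 182 days. Measuring it takes a ruler and does not require that the subject still be on drug. The protocol accepts this for partly stopped subjects, whose untreated tumors are measured to Day 182, but ends follow-up when the last treated tumor stops. No provision brings a removed subject back at Day 182.

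The 5.4 exits are related to study medication by definition. The 5.6.9 exits often may be, since local intolerance is one obvious reason for missed applications. The rules can therefore create missing outcomes that are more frequent in an active arm, and the primary analysis would compare subjects who tolerated active gel well enough to stay with nearly all vehicle subjects.

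**Working it through.** **1. What happens to a removed subject's data.** Section 7.2.1 schedules dimensions at Visits 4, 5, 6, 7 and 8, so the subject has whatever visits preceded removal plus the exit measurement. What is missing is the value at 182 ± 4 days, that is, at Day 178 (182 - 4) or later.

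**2. Does the subject enter OC?** Two readings are open.
- Exclusion: Visit 8 has a 182 ± 4 day window, and the non-responder rule in 9.3.2 speaks of terminating before Visit 8 is completed. An exit at, say, Week 10 is then not Visit 8 data.
- Inclusion: early leavers perform the Visit 8 procedures, the 6.2.8 heading covers early termination, and the per-protocol set is drawn from OC subjects who completed through Visit 8, a qualifier that would add little if OC held only completers.

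Exclusion is the better reading. Under inclusion, an early value is analyzed as Day 182. The plan gives no mapping rule.

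**3. Planned numbers (5.1, 9.1, 9.2).** 168/3 = 56 randomized per arm; 150/3 = 50 completing; allowance 56 - 50 = 6 per arm, 168 - 150 = 18 overall (18/168 = 10.7%). The stated power of at least 90% cannot be reproduced because the responder rates are redacted; this point does not depend on it.

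**4. Bound with no assumed response among removed subjects.** With k removed from an arm, k/56 of its response rate is unknown: k = 1, 1.8 points; k = 3, 5.4; k = 6, 10.7. With an assumed OC rate of 40%:
- k = 3: 0.40 × 53 = 21.2 responders, so the all-randomized rate lies between 21.2/56 = 37.9% and 24.2/56 = 43.2%.
- k = 6: 0.40 × 50 = 20, so between 20/56 = 35.7% and 26/56 = 46.4%.

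**5. Effect on a borderline result.** Pearson chi-square, no continuity correction; vehicle assumed 11/56 with none removed.

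| Removed from active | OC | Removed all non-responders | Removed all responders |
|---|---|---|---|
| 6 | 19/50, p = 0.036 | 19/56, p = 0.088 | 25/56, p = 0.005 |
| 3 | 20/53, p = 0.036 | 20/56, p = 0.057 | 23/56, p = 0.014 |

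A clearer result does not flip: 25/50 against 11/56 gives p = 0.001, and 25/56 against 11/56 gives p = 0.005.

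**6. False wins for active.** Assume the same true rate r in both arms among all 56, with every removed subject a non-responder. The OC rate in an arm losing k is r × 56/(56 - k); for k = 6 and r = 20/30/40% this is 22.4/33.6/44.8%. Summing the binomial probabilities of all tables with active higher and p < 0.05:

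| Removed (active, vehicle) | r = 20% | 30% | 40% |
|---|---|---|---|
| 0, 0 | 2.6% | 2.6% | 2.4% |
| 3, 0 | 3.5% | 3.9% | 4.9% |
| 6, 0 | 4.7% | 5.8% | 7.0% |
| 6, 2 | 4.2% | 4.6% | 4.8% |

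With 3 active and 1 vehicle removed the range is 3.0-3.6%. The same sum with six removed from each arm gives 2.5-2.8%, so balanced removals do little harm.

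All of this is at subject level. At tumor level, which is primary if the intraclass correlation is below 0.25 (9.3.5.1), each removed subject takes 10 of 560 tumors, the same 1.8% of the arm; no false-win rate was computed there.

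**The case against.** **Removals may be few.** Section 2.2.2 reports no treatment-related TEAEs in 48 subjects, and local signs and symptoms that were few and almost all mild and transient. That stands, though exposure was 28 days against 182 here. Two dose groups in the 13-week minipig study (2.2.1) were not tolerated, but concentrations are redacted, so their relevance is unknown. The six-removed case gives one arm's whole non-completion allowance to this cause, which is a stress case.

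**The plan already covers intolerance.** Section 8.1.1 makes worsening on a Target cNF assessment an adverse event if medication is interrupted or discontinued. A local-intolerance exit judged related would then count as non-response in the supplemental ITT analysis, so the adverse scenario in step 5 would be reported. This stands in part. That analysis is not primary, does not cover exits for other causes, and is defined for subject Responders. Section 9.3.5.1 promises results at both levels but does not say how missing tumors would be imputed. LOCF carries an early value forward. Optional model-based imputation could draw on stopped tumors in partly treated subjects, but those subjects were able to continue treatment elsewhere.

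**The general approach promises otherwise.** Section 9.3.1 says "All randomized and treated subjects will be assessed in analyses of safety and efficacy", which a reader might take as contradicted by OC. The same section bases analyses primarily on non-missing data, and an ITT analysis is planned, so this is not a contradiction.

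**Stronger readings the text does not support.** A reader might infer that every removal is treatment-related; the 25-day rule names no cause, so illness or travel would also qualify. A reader might infer that one untreatable tumor forces removal; the provisions for continuing with fewer tumors and for evaluating all 10 point to removal only when none can be treated. A reader might also infer that removed subjects have no outcome data, or that OC certainly excludes them; steps 1 and 2 show neither is settled by the text.

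**Conclusion.** The point holds as a cheap improvement. Sections 5.6.9 and 5.4 end follow-up when medication stops, nothing brings the subject back at Day 182, and the primary analysis imputes nothing. Under either reading of Visit 8 the primary analysis lacks the Day 182 outcome of these subjects, and no planned analysis recovers it.

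The size is conditional. Bias needs removals that are unequal between arms and outcomes among the removed that differ from those who stay; a changed conclusion also needs a borderline result. With three active-only non-responder removals, false wins for active rise from about 2.5% to 3.5-4.9%; with six, to 4.7-7.0%. The 20-40% rates, the removal counts and the vehicle count are assumptions, because the documents give no removal rate and the design rates are redacted. The documents do not show that the primary result will be biased, only that the rules leave it open to a bias that is easy to avoid.

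**What to change.** **5.6.9 and 5.4.** Replace removal from the study with a permanent stop of study medication, all 10 Target cNFs being assessed at the remaining scheduled visits through Visit 8 unless the subject withdraws consent. The safety triggers for stopping drug stay as they are.

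**5.7.2.** Apply the same, where feasible, to subjects whose blind is broken. They are now discharged, and unblinding is a plausible step after a related SAE.

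**9.3.2.** State that:
- efficacy data collected 182 ± 4 days after Visit 2 enter the primary analysis whether or not medication was stopped;
- an early-termination measurement taken fewer than 178 days after Visit 2 is not a Visit 8 observation for OC and is used in the ITT/LOCF analysis;
- the number of subjects who stopped all medication is reported by arm and reason.

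**Cost.** A protocol amendment with sponsor and IRB/EC approval (12.4), and the remaining scheduled visits for those who stop early, at most about 18 subjects on the planned allowance. No new assessments and no change to sample size. The change has to be made while subjects are still in follow-up, because a Day 182 value that was not taken cannot be obtained later.

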5.6.10 Accountability

The investigator or designee will maintain an accurate record of the receipt of the study medications as shipped by NFlection or designee, including the date received and the condition of the study medications. One copy of this receipt will be returned to NFlection when the contents of the study medication shipment have been verified and one copy maintained in the study file. In addition, an accurate study medication disposition record will be kept, specifying the amount dispensed to each subject and the date of dispensing. This inventory record will be available for inspection at any time. At the completion of the study, the original inventory record will be available for review by NFlection upon request.

5.6.11 Return and disposition of study medication

At the completion of the study, all unused study medication will be returned to NFlection or designee for disposal per NFlection or designee's written instructions unless returned study medication is destroyed by the site according to applicable SOP.

5.7 Blinding

5.7.1 Verification of blinding

Blinding of the study medications is important for validity of this study. This study uses a double-blind design. The study medications are indistinguishable in appearance, packaging and labeling.

5.7.2 Unblinding the study medication

Blinding is important for validity of this study; however, the blind may be broken in the event of a medical emergency in which knowledge of the study medication identity is critical to the management of the subject's course of treatment. Before breaking the blind, the investigator should determine that the information is necessary (*i.e.*, that it will alter the subject's immediate course of treatment). In many cases, particularly when the emergency is clearly not study

medication-related, the problem may be effectively managed by assuming that the subject is receiving active study medication without the need for unblinding.

If deemed necessary to break the blind for a study subject, attempt to contact the Medical Monitor to obtain concurrence. If it is not possible to contact the Medical Monitor beforehand, contact her/him as soon as possible after breaking the blind for a subject.

To identify a subject's study medication, locate the second panel of the Subject Kit tear-off label attached to the subject's CRF and follow the unblinding instructions on the label. Record the date of unblinding, the reason for unblinding and the initials of the investigational center staff member who performed the unblinding in the subject's CRF.

Any subject whose blind has been broken must be discharged from the study.

5.8 Study medication adherence

Adherence with the study medication application frequency and application of an appropriate amount of study medication will be monitored by questioning the subject regarding adherence at each visit and by measuring the weight of the study medication tubes when dispensed to the subject, at each treatment period visit and when collected from the subject.

5.9 Subject instructions

At Visit 1, an investigational center staff member will dispense a Subject Instruction sheet to each subject.

During the entire duration of the study subjects must:

- Continue to use her/his routine cleansers and cosmetics
- Not apply any topical products, including the study medication to any Target cNF within 6 hours prior to a study visit
- Minimize exposure of Target cNFs to sunlight and use her/his routine sunscreen if exposure cannot be avoided
- Not use tanning beds
- Bring the subject instruction sheet to every visit.

During the 182-day (26-week) treatment period, subjects must:

- Apply the study medication to each Target cNF as directed, once daily, with 18-30 hours between applications

- Not apply the study medication to any open wounds or obviously infected skin
- Not wash or submerge any Target cNF for at least 6 hours after a study medication application
- Not apply the study medication, to any Target cNF within 6 hours prior to a study visit, , except on Visit 4 when the subject should apply study medication 4 (\pm 2 hours) prior to the scheduled appointment time.
- Not apply any topical products to any Target cNF within 6 hours prior to a study visit
- Not apply any topical products to any Target cNF for at least 6 hours after a study medication application
- Not allow anyone else to use your study medication
- Keep the study medication away from children
- Store the study medication at room temperature
- Bring all study medication tubes to every visit.

5.10 Other study supplies

In addition to the equipment and supplies provided for performing study procedures, such as blood sampling, urine pregnancy tests and photography, NFlection, or designee, will provide the following items to each investigational center prior to the initiation of subject enrollment:

- Rulers for measuring each Target cNF
- Scales for weighing the study medication tubes.

6.2.1 Visit 1/Day -28 to 0/Week -4 to 0 (Screening)

At Visit 1, the investigator or designee will:

1. Review and explain the nature of the study to the subject, obtain the subject's signature on the appropriate approved ICF and Health Insurance Portability and Accountability Act (HIPAA) authorization and provide a signed and dated copy to the subject
2. Assign a Subject Identifier to the subject
3. Confirm the subject meets all inclusion criteria and no exclusion criteria
4. Collect demographic and medical history information
5. Report concomitant therapies information
6. Conduct a physical examination
7. Measure vital signs
8. Collect samples for clinical laboratory tests
9. Perform a urine pregnancy test for WOCBP
10. Identify 10 clinically diagnosed Target cNFs (preferably 2 Target cNFs located on the face and 8 Target cNFs are located on the anterior trunk or upper extremities. Alternatively, at least 1 Target cNF is located on the face, in which case 9 Target cNFs must be located on the anterior trunk or upper extremities)
11. Create Visit 1 body charts and dispense a photocopy to the subject
12. Perform a Physician's Tumor Assessment (PTA) on each Target cNF and confirm each meets the enrollment criteria
13. Measure the dimensions of each Target cNF and confirm each meets the enrollment criteria
14. Take standardized photographs of each Target cNF
15. Review the study instructions with the subject and dispense a Subject Instruction Sheet
16. Schedule Visit 2.

6.2.2 Visit 2/Day 1/Week 0 (Randomization; start of QD treatment)

Visit 2 must occur within 28 days (4 weeks) after Visit 1.

Subsequent study visit dates must be scheduled based on the date of this visit.

This visit may be combined with Visit 1 and only with advance Sponsor approval. If combined with Visit 1, central laboratory samples must be collected along with local laboratory samples.

Randomization must not occur until the investigator reviews the subject's Visit 1 clinical laboratory test results or local laboratory test results, if applicable.

At this visit, the investigator or designee will perform the following procedures PRIOR TO RANDOMIZATION:

1. Query the subject in a non-directive manner about any changes in her/his health since the previous visit and report any changes as medical history

2. Query the subject about any changes in her/his concomitant therapies since the previous visit and report changes as appropriate
3. Confirm the subject meets all inclusion criteria and no exclusion criteria
4. Confirm the subject has followed all study instructions
5. Perform a urine pregnancy test for WOCBP
6. Collect Visit 1 body charts
7. Create Visit 2 body charts and dispense a photocopy to the subject
8. Confirm the location of each Target cNF identified
9. Measure the dimensions of each Target cNF
10. Have the subject perform a Subject's Self-Assessment (SSA) for each Target cNF
11. Perform a PTA for each Target cNF
12. Confirm subject is eligible for randomization, discharge subjects who are not eligible from the study.

Determine the subject's eligibility for randomization. Ineligible subjects must be discontinued from the study. For eligible subjects the investigator or designee will perform the following procedures:

1. Have the subject perform a pre-application Local Tolerability Assessment (LTA) of the symptoms for each Target cNF
2. Have the subject perform a Patient Reported Outcome Measure (PROM) for each Target cNF
3. The investigator will perform a pre-application LTA of the signs for each Target cNF
4. Take standardized photographs of each Target cNF
5. Measure vital signs
6. Collect samples for clinical laboratory tests
7. Randomize eligible subjects
8. Weigh study medication tube pre first study medication application and record weight
9. An investigational center staff member must:
 - Instruct the subject on the proper study medication application technique
 - Observe the subject's first study medication application to each Target cNF and record the Application Completion Time
 - Weigh the study medication tube POST first study medication application and record weight
 - Dispense study medication
 - Monitor the subject for adverse events for at least 20 minutes after the Application Completion Time
10. Have the subject perform a post-application LTA of the symptoms for each Target cNF 10 (± 4) minutes after the Application Completion Time
11. The investigator will perform a post-application LTA of the signs for each Target cNF 20 (± 4) minutes after the Application Completion Time
12. Review the study instructions with the subject
13. Schedule Visit 3.

